### 3. GENERAL INFORMATION

Objective	
The objective of the current study is to prospectively evaluate 3-month clinical outcomes from LASIK performed using the Phorcides surgical planning software with Contoura topography-guided ablation in both eyes of subjects with myopia and myopic astigmatism seeking refractive surgery for distance correction. Data will be compared to published results for wavefront optimized LASIK and LASIK performed with Contoura using other refractive algorithms.
 
The hypothesis is that use of the Phorcides planning software will result in a higher percentage of eyes with residual refractive cylinder <math>\leq 0.25D</math> than will be achieved with wavefront-optimized (WFO) LASIK. It is also expected that unaided postoperative visual acuity and visual symptoms will be improved.

Test Article(s)	Phorcides Analytical Engine refractive surgery planning software
Control Article(s)	None
Sample size	140 eyes of 70 subjects
Study Population	Subjects $\geq 20$ years of age with myopia and myopic astigmatism, who are suitable candidates for LASIK, meet the approved range of treatment for Contoura topography-guided LASIK and desire optimal uncorrected distance visual acuity in both eyes.
Number of sites	Four
Study Design	Prospective, single arm, open-label study.
Masking	None
Variables	Primary: 

● Residual refractive cylinder

 Secondary: 

● Monocular uncorrected distance visual acuity

- Monocular corrected distance visual acuity
- Residual refractive sphere
- Corneal aberrations
- Ocular aberrations (at sites equipped for such measurement)
- Subjective questionnaire evaluating visual symptoms such as light sensitivity glare, halos, and starbursts

Duration / Follow-up    Preoperative to 3 months postoperative

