## **8. STUDY DESIGN**

The study is a prospective, single-arm open clinical trial to evaluate residual refractive error and distance visual acuity after excimer laser treatment for the correction of refractive error to produce good uncorrected distance vision. All eyes enrolled will have surgery planned with Phorcides and treated using the Contoura topography-guided surgery algorithm.

Subjects will be assessed pre-operatively and at 1 day, 1 month and 3 months post-operatively.

Clinical evaluations at 1 month and 3 months will include measurement of uncorrected distance visual acuity (UCDVA), manifest refraction, and corrected distance visual acuity (CDVA). At 3 months, corneal aberrations will be measured, and subjects will complete a questionnaire evaluating satisfaction with their visual outcome, quality of vision, and visual symptoms (light sensitivity, difficulty driving at night, reading difficulty, fluctuation in vision, glare, halos, and starbursts).

The primary outcome measure will be the residual refractive cylinder.

Secondary outcome measures will be the following:

- Uncorrected distance visual acuity
- Residual sphere
- Corneal aberrations
- Ocular aberrations, at sites with the appropriate equipment to measure such.
- Satisfaction with the visual outcome, quality of vision, and visual symptoms (light sensitivity, difficulty driving at night, reading difficulty, fluctuation in vision, glare, halos, and starbursts).

Safety measures will be

- Change in corrected distance visual acuity
- Satisfaction with the visual outcome, quality of vision, and visual symptoms (light sensitivity, difficulty driving at night, reading difficulty, fluctuation in vision, glare, halos, and starbursts).

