### ***8.2. Methods Used to Minimize Bias***

This is a single-arm study with both eyes of any subject enrolled. Patients will not be pre-selected for study inclusion. Any eligible patient presenting for, and eligible for, binocular Contoura treatment may be invited to participate.

The measurement of the postoperative refraction and visual acuity will be conducted in a systematic fashion to minimize bias. Individuals conducting visual acuity measures will be refracted with the methodology used in the Early Treatment Diabetic Retinopathy Study, with the same level of encouragement to subjects. Subjective questions will be asked in a similar manner to all patients. Alternatively, at the discretion of the investigator, patients may be asked to complete the questionnaire themselves.

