**Table 9.3-2. Testing Schedule**

Test	Visit				
	1	2	3	4	5
UCVA	X		X	X	X
MR	X			X	X
CDVA	X			X	X
Slit lamp exam	X	X	X	X	X
Fundus exam	X*				X
IOP	X			X	X
Topography	X			X	X
Ocular HOA (site specific)	X				X
Questionnaire	X				X

\*Not required if fundus exam has been performed by any physician within 6 months and results are available for review by the investigator.

All data will be recorded on the provided CRFs. All site personnel involved in the study will be trained to follow the study protocol, conduct study-specific procedures, and record data properly. CRFs will be identified by the subject number assigned at each site. No protected health information (PHI) will be included on any CRF, but a separate record of patient names and study identifying numbers will be maintained at each investigational site.

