#### 9.4.1. Manifest refraction

Perform a manifest refraction with a high contrast logMAR ETDRS chart under photopic lighting conditions ( $>85$  cd/m^2). Document refraction results with sphere, cylinder and axis readings using the ETDRS protocol. If uncorrected visual acuity is not improved by manifest refraction, use zero for sphere and cylinder and draw a line through the blank for the axis. All visual acuities should be recorded as letters read on the ETDRS chart.

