#### 9.4.4 Ocular high order aberrations

Measure ocular HOA at sites appropriately equipped to do so. The device used to measure HOA's should be indicated, and a 5 mm pupil size should be selected where feasible.

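### The 0.25 D hypothesis rests on an open-label manifest refraction: the method is standardised, but earlier refractions are not withheld from the Visit 5 examiner and no objective cylinder is planned as a check

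*Combined protocol and SAP*

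**What the plan says.** The synopsis (section 3) describes a "Prospective, single arm, open-label study" and gives masking as none. Section 8 states: "The primary outcome measure will be the residual refractive cylinder". It attaches no cut-off. The cut-off is in the synopsis: "The hypothesis is that use of the Phorcides planning software will result in a higher percentage of eyes with residual refractive cylinder" at or below 0.25 D than wavefront-optimised LASIK achieves. The comparison is with published results (sections 3 and 6).

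The only refraction scheduled is the manifest refraction, at Visits 1, 4 and 5 (Tables 9.3-2 and 15.1). Section 8.2 says "The measurement of the postoperative refraction and visual acuity will be conducted in a systematic fashion to minimize bias". Section 9.4.1 specifies a high-contrast ETDRS chart in photopic light and adds "Document refraction results with sphere, cylinder and axis readings using the ETDRS protocol". It also has a recording rule: "If uncorrected visual acuity is not improved by manifest refraction, use zero for sphere and cylinder". The text under Table 9.3-2 requires site personnel to be trained in the study procedures.

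For ocular aberrations, section 9.4.4 says "Measure ocular HOA at sites appropriately equipped to do so". It asks that the device be indicated but names none. Both schedules place this measurement at Visits 1 and 5, and section 8 lists it as a secondary outcome. Section 10 contains no agreement or sensitivity analysis of the cylinder result.

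**The concern.** A manifest refraction depends on the judgement of both patient and examiner. An examiner who can see the preoperative refraction, the programmed treatment or the Visit 4 result may be drawn towards an expected value. With a cut-off as low as 0.25 D, a small leaning in a few eyes changes the percentage on which the hypothesis is stated. No concurrent arm is refracted by the same staff, so nothing inside the study would reveal or cancel such a leaning. The introduction (section 5) states in advance that superior results are expected, so a reader of the eventual paper is likely to ask how the cylinder was protected.

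**Working it through.** **The text, side by side.**
- Standardisation of method: present. Section 9.4.1 covers sphere, cylinder and axis; section 8.2 promises systematic conduct of both refraction and acuity. The next sentence of 8.2 is garbled (taken literally, the people measuring acuity are the ones refracted), but 9.4.1 makes the intended method clear.
- Withholding of earlier values: absent from 8.2, 9.3.3 and 9.4.1. Table 9.3-1 gives each visit its own CRF, so a fresh form exists, but nothing addresses the clinic chart or the treatment plan.
- Objective check on cylinder: absent. Topography and Pentacam corneal aberrations are objective but corneal, and they are not planned as a check on refractive cylinder.
- Zero rule: it acts in one direction, because a recorded zero always falls at or below 0.25 D. The documents do not show how often it would apply.

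**The plan's own figure.** Section 11: 140 × (1 − 0.10) = 126 eyes, which reproduces. One eye is 1/126 = 0.8 percentage points. No benchmark rate, effect size or power is given.

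**Illustration 1: shift in the percentage.** Assume recording in 0.25 D steps, which the documents do not state. Shift = (share of eyes truly at 0.50 D) × (share of those recorded one step lower).
- 15% at 0.50 D: 0.15 × 0.10 = 1.5 points; 0.15 × 0.50 = 7.5 points.
- 20% at 0.50 D: 0.20 × 0.10 = 2 points; 0.20 × 0.50 = 10 points.

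All four inputs are assumed, and every misreading is taken to go downward.

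**Illustration 2: what a shift could do.** Assume 126 independent eyes, a fixed benchmark, a true rate equal to it, and an exact binomial upper tail of at most 0.025 (the upper half of a two-sided 5% test). The last three columns give the chance of a false superiority finding.

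| Benchmark | Expected eyes | Eyes needed | Gap | No shift | +2 points | +5 points |
|---|---|---|---|---|---|---|
| 60% | 75.6 | 87 | 11.4 | 0.022 | 0.061 | 0.196 |
| 70% | 88.2 | 99 | 10.8 | 0.020 | 0.059 | 0.207 |
| 80% | 100.8 | 110 | 9.2 | 0.022 | 0.072 | 0.281 |
| 90% | 113.4 | 121 | 7.6 | 0.011 | 0.057 | 0.394 |

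Two cautions apply. At a true rate of 90%, at most 10% of eyes can be at 0.50 D, so a 5-point shift needs at least half of the eyes above the cut-off to be misread; that row is an extreme. The table also ignores the correlation between a subject's two eyes and any similar bias in the benchmark.

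**The case against.** The case against is substantial, and much of it stands.

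- A reader might infer that the safeguards in 8.2 protect only visual acuity. They do not stop there: 8.2 names refraction, and 9.4.1 applies the ETDRS protocol to cylinder and axis. The gap is confined to sight of earlier values and the lack of an objective comparison.
- A reader might take 0.25 D as the definition of success for the primary endpoint. The cut-off appears in the hypothesis only, and no section defines success.
- A reader might infer that equipped sites already obtain an objective cylinder that the plan discards. No device is named, the number of equipped sites is not given, and nothing says that the device reports cylinder. The proposal must therefore depend on the device.
- Published comparators may also rest on unmasked refraction, which would offset part of any bias. The net direction is unknown.
- Refracting without earlier values leaves the examiner aware that every eye was planned with Phorcides. That is inherent in a single-arm study.
- Objective and manifest cylinder can differ for reasons of method, so disagreement would not by itself show examiner bias.

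None of this supplies the missing instruction. That instruction is useful even if no site has a suitable aberrometer.

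**Conclusion.** The concern holds in a limited form. The quantity behind the 0.25 D hypothesis is an open-label subjective refraction with a standardised method, but the Visit 5 examiner is not shielded from earlier values and no objective cylinder is planned beside it.

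Its size cannot be fixed from the documents. The range of 1.5 to 10 points and the false-superiority chances show only that a shift of a few eyes could matter; they are not estimates for this trial. They rest on assumed 0.25 D steps, assumed shares and benchmarks, independent eyes and one-directional misreading. It would be wrong to conclude that the trial's percentage will be inflated by such an amount, or that the open-label design is a concealed flaw: the protocol declares it. This is a worthwhile low-cost improvement to what the trial can conclude.

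**What to change.** 1. In 8.2 and 9.4.1, state that the usual staff perform and record the Visit 4 and Visit 5 manifest refractions without sight of the preoperative refraction, the programmed treatment or earlier postoperative refractions. Describe this as a limit on anchoring, not as masking of the treatment.
2. In 9.4.4, add that where the site's aberrometer reports cylinder and axis, both are recorded from the Visit 5 capture.
3. In section 10, prespecify a supportive table for those eyes: objective beside manifest cylinder at Visit 5, with the share at or below 0.25 D by each.

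Cost: one training instruction, two CRF fields and one table, with no added staff, visit or procedure. Downside: the objective comparison covers equipped sites only, and objective cylinder may differ systematically from manifest cylinder. The table is therefore supportive and cannot replace the primary result.

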## **9. STUDY PROCEDURE**

### ***9.1. Informed Consent / Subject enrollment***

No subject will be enrolled into the study who does not meet the inclusion/exclusion criteria and does not sign the current approved informed consent document. Informed consent will be obtained prior to collecting any data for the study. The original signed documents will be maintained by the investigator as a permanent part of the subject's medical records. A signed copy will be provided to the subject.

Subjects will each receive a rebate of their refractive surgery payment when they complete the 3-month visit. This rebate will amount to \$250 per eye, so subjects will receive a \$500 rebate in total.

**9.2. Surgery Procedures**

Following a complete ophthalmic examination (history, visual acuity, refraction, slit-lamp exam, fundus exam, topography), patients who meet inclusion criteria and choose to participate in the study after informed consent will be brought to the operating room where bilateral LASIK will be performed using the techniques routinely used by each investigator.

**9.3. Visits and Examinations**

Subjects will participate in five study visits. Visits will include a preoperative/enrollment visit (Visit 1), one operative visit (Visit 2), and 3 postoperative visits (Visit numbers 3, 4, and 5). The preoperative visit and operative visit may occur on the same day if a fundus exam has been performed within the previous 6 months and the findings are available at the time of the preoperative/operative visit. The visit schedule, visit windows, and associated Case Report Forms (CRFs), are displayed in Table 9.3-1. Details of each study visit, including testing to be conducted, are provided in Table 9.3-4 and below.

**Table 9.3-1. Visit Schedule**

Visit Number	Visit Name	Visit Window	CRF Number
1	Preoperative	-30 to 0 days before surgery	1
2	Operative	0 from surgery	2
3	1 Day Postoperative	1-7 days after surgery	3
4	1 Month Postoperative	1 month (1 month – 2 ½ months)	4
5	3 Months Postoperative	3 months (2 ½ - 5 months) after surgery	5

**Table 9.3-2. Testing Schedule**

Test	Visit				
	1	2	3	4	5
UCVA	X		X	X	X
MR	X			X	X
CDVA	X			X	X
Slit lamp exam	X	X	X	X	X
Fundus exam	X*				X
IOP	X			X	X
Topography	X			X	X
Ocular HOA (site specific)	X				X
Questionnaire	X				X

\*Not required if fundus exam has been performed by any physician within 6 months and results are available for review by the investigator.

All data will be recorded on the provided CRFs. All site personnel involved in the study will be trained to follow the study protocol, conduct study-specific procedures, and record data properly. CRFs will be identified by the subject number assigned at each site. No protected health information (PHI) will be included on any CRF, but a separate record of patient names and study identifying numbers will be maintained at each investigational site.

### 9.3.1. Preoperative

Subjects who meet inclusion criteria and provide informed consent will undergo the following procedures.

- Medical history
- Testing as shown in Table 9.3-2 as described in Section 9.4 below
- Site-specific, routine preoperative procedures and measurements

### 9.3.2. Operative (Surgery)

Preoperative examination and testing procedures (with the exception of the fundus examination) may be performed or repeated on the operative day at the discretion of the investigator. A brief slit lamp examination will be performed. The patient will then be brought into the operating room, where bilateral LASIK surgery (planned using the Phorcides analytical engine) will be performed with routine procedures specific for each site.

Surgical findings will be recorded and any adverse events/serious adverse events (AEs/ SAEs) occurring during surgery will be noted at this visit. Any other problems encountered during surgery and comments regarding surgery will be documented.

Any complications preventing successful completion of surgery will be documented, and any subject whose surgery is not completed successfully will be excluded from further participation in the study and followed according to procedures that are standard for each individual study site.

Postoperatively, patients will be managed according to standard procedures for each individual study site.

### 9.3.3. Postoperative Day 1, Month 1, and Month 3

All routine postoperative procedures and measurements will be performed according to the standard operating procedures for each study site. Testing will be performed as specified in Table 9.3-2 above and Section 9.4 below. Adverse events will be monitored and documented. Additional tests specific for this study will be administered at Visit 5.

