### **7.4. Exclusion Criteria during surgery**

The following exclusion criteria are applicable to the study eye during the study

- Intraoperative complications.

Any subject whose surgery has been aborted for either eye should immediately be discontinued from the study and an exit form completed for that subject. These subjects will be followed according to the clinic standard of care and monitored for safety, but their data will be excluded from the study efficacy analysis. All adverse events will be appropriately documented and reported.

Participants who are considered to be in a vulnerable population will not be enrolled into the study. Vulnerable populations include, but are not limited to, the following:

- Prisoners
- Nursing home residents
- Institutionalized individuals
- Mentally disabled and cognitively impaired individuals
- Sponsor employees and their family members
- Site employees and their family members that are directly or indirectly involved in the study
- Economically disadvantaged individuals
- Educationally disadvantaged individuals
- Adults who do are illiterate
- Subjects who are deaf or have a severe hearing disability
- Terminally ill individuals
- Individuals with life-threatening conditions

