## **10. ANALYSIS PLAN**

### **10.1. *Analysis Data Sets***

All subjects who are enrolled in the study will be evaluated for safety. Efficacy analyses will be performed based on data from those eyes for which uncomplicated LASIK was completed.

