## 15. STANDARD EVALUATION PROCEDURES

**Table 15.1. Proposed Visits and Study Assessments**  
 (visits are by patient, with both eyes tested)

Activity	Pre-operative	Operative	Postoperative		
	Visit 1	Visit 2	Visit 3	Visit 4	Visit 5
			1 Day	1 Month	3 Months
Informed consent	X				
Demographics	X				
General information: medical history	X				
Surgery		X			
Manifest refraction	X			X	X
Uncorrected distance VA (monocular)	X		X	X	X
Corrected distance VA (monocular)	X			X	X
Corneal aberrations	X				X
Ocular aberrations (site specific)	X				X
Subjective questionnaire	X				X
Monitor for adverse events		X	X	X	X
Complete Exit Form 					X

 Complete Exit Form upon termination of subject participation, or at Visit 5, whichever occurs first.

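### Subjects whose surgery is aborted or unsuccessful in either eye leave the study at Visit 2, so neither eye has a required postoperative CDVA or questionnaire, although both are named safety measures

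*Combined protocol and SAP*

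**What the plan says.** Two sections of the combined protocol and SAP set the rule. Section 7.4: "Any subject whose surgery has been aborted for either eye should immediately be discontinued from the study and an exit form completed for that subject". Section 9.3.2, describing the operative visit: "any subject whose surgery is not completed successfully will be excluded from further participation in the study". Both act on the subject, not the eye.

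Section 7.4 says what happens next. The subjects are "followed according to the clinic standard of care and monitored for safety, but their data will be excluded from the study efficacy analysis", and their adverse events are still documented and reported. Section 9.3.2 likewise leaves follow-up to each site's standard procedures.

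Section 8 names two safety measures. One is "Change in corrected distance visual acuity". The other is "Satisfaction with the visual outcome, quality of vision, and visual symptoms". Tables 9.3-2 and 15.1 schedule CDVA at Visits 1, 4 and 5, and the questionnaire at Visits 1 and 5.

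Section 10.1 states: "All subjects who are enrolled in the study will be evaluated for safety". It restricts efficacy to eyes with completed, uncomplicated LASIK. It does not say which safety measures a subject discontinued at surgery contributes.

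**The concern.** Taken together, these sections remove a subject from the schedule before any postoperative value of either named safety measure is due. The missing data are tied to how the surgery went, unlike ordinary dropout. The event itself will be recorded. Its effect on best-corrected vision at 1 and 3 months need not be measured, or measured in the same way across four sites.

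The fellow eye is the clearest case. If the first eye is fully treated from a Phorcides plan and the second is aborted, the treated eye also loses its scheduled CDVA. That eye received the test article, so its safety outcome is directly relevant.

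At stake is the CDVA-change summary, which would omit the cases in which surgery went wrong. If loss of CDVA is more common in those cases than in completed ones, the summary will look somewhat better than the experience of all eyes in which surgery was started.

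**Working it through.** **Step 1: what is scheduled after surgery** (Tables 9.3-1, 9.3-2 and 15.1)

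| Measure | Visit 1 (preop) | Visit 2 (surgery) | Visit 3 (1 day) | Visit 4 (1 month) | Visit 5 (3 months) |
|---|---|---|---|---|---|
| CDVA | X | | | X | X |
| Questionnaire | X | | | | X |

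A subject discontinued at Visit 2 has a baseline for both measures and no scheduled postoperative value for either.

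**Step 2: does any other section restore the measurement?**

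- Section 7.4 (clinic follow-up and safety monitoring): names no CDVA and no time point.
- Section 9.3.4 (premature exit): asks for the study examinations where possible and gives no date. Exit here falls around the operative day, so an exit examination cannot supply a 1- or 3-month value.
- Section 9.6 (discontinued subjects): asks for an assessment and advice on care; names no CDVA and no time point.
- Sections 13.1 to 13.3 (adverse events): an apparent visual loss could be reported, but no CDVA threshold defines an event, and the inquiry in 13.2 asks only whether the patient has problems.
- Section 13.4: data from whatever follow-up takes place must be documented and available; CRF entry is left to judgment. It does not require the measurement.

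None requires CDVA at 1 or 3 months or the questionnaire at 3 months.

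**Step 3: how many subjects**

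Inputs from the plan: 70 subjects and 140 eyes (section 7.1); 10% dropout (section 11); replacement of subjects lost before surgery (section 18.2), so 70 operated subjects are used. The plan's own figure reproduces: 140 × (1 − 0.10) = 126 eyes, a planned loss of 14 eyes.

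The documents give no rate of aborted or unsuccessful surgery. I assume q = 0.5%, 1% or 3% of subjects and take X ~ Binomial(70, q). The expected count is 70q, and P(X ≥ 1) = 1 − (1 − q)^70.

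| Assumed q | Expected subjects | Upper bound on expected eyes (× 2) | P(X ≥ 1) | P(X ≥ 3) | 95th percentile |
|---|---|---|---|---|---|
| 0.5% | 0.35 | 0.7 | 0.296 | 0.005 | 1 |
| 1% | 0.70 | 1.4 | 0.505 | 0.033 | 2 |
| 3% | 2.10 | 4.2 | 0.881 | 0.351 | 5 |

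The eye count is an upper bound, because a second eye may never have been started. One eye is 1/140 = 0.7% of the planned eyes. No rate of CDVA loss after an abort is assumed, so the effect on the summary itself cannot be computed.

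**The case against.** The strongest reply is that safety is already looked after. These subjects stay under clinic care and are monitored, their adverse events are reported, exit examinations are encouraged, and section 10.1 keeps them in the safety evaluation. That stands, and it limits the point. A reader might infer from the discontinuation rule that safety follow-up stops; section 7.4 says the opposite. What remains is that two named measures are not required at their scheduled times.

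It can also be said that the plan defines no rate of CDVA loss. Section 8 names only change in CDVA, and section 13.5 tabulates adverse events without mentioning it. This stands too: what is affected is a descriptive summary.

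Third, an eye that received no ablation says little about a planning tool. That is fair, and such eyes should be shown separately. It does not apply to a fully treated fellow eye.

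Fourth, a reader might suppose that section 10.1 already keeps these subjects out of the efficacy set, so that follow-up could simply be extended. It does not. Its efficacy definition is by eye, and a successfully treated fellow eye meets it; the subject-level exclusion comes from section 7.4. Collecting 3-month data on that eye would expose the mismatch.

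Fifth, section 18.3 terminates a patient for a severe adverse event that may be related to the study and counts the patient as having completed it. Amending sections 7.4 and 9.3.2 alone could therefore still lose these values. The last two objections are correct and shape the fix.

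**Conclusion.** The point holds in a limited form. For subjects whose surgery is aborted or not completed successfully in either eye, the plan requires no postoperative CDVA or questionnaire for either eye, although section 8 names both as safety measures and section 10.1 includes these subjects in the safety evaluation.

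The size is unknown and probably small: 0.35 to 2.1 subjects expected, resting on an assumed 0.5% to 3% per subject, against 14 eyes of planned dropout. No test or success criterion depends on it.

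Two stronger readings should be set aside. A reader might infer that the omission flatters the study against the published comparators; the documents do not say how those studies handled aborted cases, so no direction can be claimed. A reader might also extend the point to surgery completed despite a complication. Section 7.4 lists intraoperative complications as an exclusion criterion, but its explicit discontinuation sentence covers only aborted surgery, so that case is not settled by the text and is not part of this finding.

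Cheap improvement, low priority.

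**What to change.** 1. **Sections 7.4 and 9.3.2.** Exclude the subject from efficacy only. Keep the subject on the safety assessments already scheduled at Visits 3 to 5, including CDVA at Visits 4 and 5 and the questionnaire at Visit 5, unless consent is withdrawn or the investigator judges that continuing poses a health risk (section 9.6). Complete the Exit form at Visit 5.
2. **Section 10.1.** State that efficacy excludes both eyes of any subject with an aborted or unsuccessful surgery, to match section 7.4. Report CDVA change for all eyes in which surgery was started, showing aborted or unsuccessful cases separately and noting for each eye whether ablation was delivered.
3. **Section 18.3.** State that termination for a severe related adverse event does not end the scheduled safety CDVA and questionnaire.
4. **Timing.** Time Visits 3 to 5 from the date of the surgery at Visit 2. For any re-treated eye, record the re-treatment date and report the last CDVA before it alongside the 3-month value.

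Clinical care, including re-treatment, stays as each site decides.

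**Cost.** Protocol wording, plus up to three extra CRF visits per affected subject: 3 × 0.35 = 1.05 to 3 × 2.1 = 6.3 in expectation, and 3 × 5 = 15 for five subjects (the 95th percentile at an assumed 3%). If the rebate in section 9.1 is paid, that is $500 × 0.35 = $175 to $500 × 2.1 = $1,050 in expectation, and $2,500 for five subjects. The safety figures may look slightly less favourable.
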